4.3 Secondary Outcomes Analysis

For the secondary outcomes outlined in section 2.2.1, a chi-squared test of independence will be used to compare the proportions between groups where appropriate. Odds ratios with 95% confidence intervals, and p values will be reported.

Hospital-free days alive, ICU-free days alive, ventilator-free days and organ support-free days will be respectively analyzed as: the number of days out of hospital alive; the number of days out of ICU alive; the number of ventilator-free days alive (alive and free of invasive mechanical ventilation); and the number of organ support-free days alive (alive and free of invasive mechanical ventilation, non-invasive mechanical ventilation, high flow nasal cannula oxygen and vasopressor therapy) through day 28;

death up to 28 days will be assigned a value of -1. These outcomes will be analyzed using ordinal logistic regression.

The post-treatment D-dimer will be compared by means of linear regression (ANCOVA), adjusted for baseline. Since the D-dimer assay differed across sites, the raw values are not comparable. Therefore, the D-dimer will be analyzed as the logarithm of D-dimer x upper limit of normal (ULN) by taking the natural logarithm of the ratio of the actual d-dimer value divided by the ULN for the assay used.

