#### ***7.2 Statistical Analysis***

Primary analyses will be by in the intention-to-treat population of all randomized patients in accordance with the originally allocated intervention. We will conduct a chi-square test for the main analysis of the primary outcome and use a generalized linear regression model with binary distribution and identity link to derive risk difference with 95% confidence intervals. We will conduct subgroup analyses accompanied by tests of interaction for the following variables: age, sex, BMI, time from COVID-19 symptom onset, diabetes mellitus, coronary artery disease, hypertension and race/ethnicity. Logistic regression and linear regression will be used to analyse binary and continuous secondary outcomes after adjustment for age (used for stratification of randomization). Secondary outcomes are exploratory and will not be adjusted for multiple comparisons. A per-protocol analysis of the primary outcome will be restricted to the per-protocol population of participants, defined as those who received experimental or control intervention as allocated during the first 48 hours after randomization. The analysis of safety outcomes will be done in both, the intention-to-treat and per-protocol populations.

If an outcome is missing in more than 5% of the patients, in addition to the pre-planned strategy of assuming non-outcome if patients were discharged alive from hospital before 28 days, a complete case analysis, an inverse probability weighted analysis and multiple imputation on outcome will also be conducted. The statistical analysis plan will be finalized prior to study closure without prior inspection of the data. All analyses will be conducted in Stata version 15.1.

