4.2 Primary Outcome Analysis

The primary analysis will compare the proportions of subjects experiencing the composite outcome within 28 days after randomization between the 2 treatment arms (therapeutic doses of LMWH or high dose nomogram of UFH versus standard care). Difference in proportions and the 95% confidence interval will be reported. A Chi-squared test of independence will be conducted to obtain the p-value. Since randomization was stratified by age a logistic regression model will also be fit to obtain and test the treatment effect adjusting for age. These two complementary analyses are being performed since an adjusted analysis result in a different interpretation of the treatment effect (conditional) versus the unadjusted (marginal or population averaged). Although the protocol specifies binomial models with an identity link, these were found to not converge by the unblinded statistician while preparing DSMB reports. Therefore, the more stable logistic regression model will be used. Since two interim analyses were conducted, the level of significance at which the Chi-squared test of independence is conducted is 0.048 (two-sided).

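### SAP 4.3 leaves out, without explanation, the age adjustment that Protocol 7.2 specifies for the secondary outcomes

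*SAP*

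**What the plan says.** **Protocol 7.2:** "Logistic regression and linear regression will be used to analyse binary and continuous secondary outcomes after adjustment for age (used for stratification of randomization"). The same section makes an unadjusted chi-square test the main analysis of the primary outcome and calls the secondary outcomes exploratory, with no multiplicity adjustment.

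**SAP 4.3, binary outcomes:** "For the secondary outcomes outlined in section 2.2.1, a chi-squared test of independence will be used to compare the proportions between groups where appropriate", and then "Odds ratios with 95% confidence intervals, and p values will be reported". No model for the odds ratio is named.

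**SAP 4.3, four free-day outcomes:** "These outcomes will be analyzed using ordinal logistic regression". No covariate is named.

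**SAP 4.3, D-dimer:** "The post-treatment D-dimer will be compared by means of linear regression (ANCOVA), adjusted for baseline". Age is not named.

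**SAP 4.2, primary outcome:** "A Chi-squared test of independence will be conducted to obtain the p-value", and in addition "Since randomization was stratified by age a logistic regression model will also be fit to obtain and test the treatment effect adjusting for age". The SAP presents these two analyses as complementary, one marginal and one conditional.

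**The concern.** Two governing documents give different analyses of the same outcomes, and nothing says which one holds. For 28-day death, a reader can find an age-adjusted logistic model in the protocol and an unadjusted test in the SAP.

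The SAP discloses other departures. It explains why the identity-link model was dropped, and it marks the outcomes and subgroups that the protocol did not list. It gives no reason for leaving age out of 4.3. The convergence problem reported in 4.2 is not a reason, because the protocol's secondary model is already logistic, the form that the SAP adopts as the more stable one.

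SAP 4.2 justifies its extra model by the stratified randomisation, and the secondary outcomes come from that same randomisation. SAP 4.2 also says that marginal and conditional effects are interpreted differently, yet 4.3 does not say which kind of odds ratio it will report.

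Death and major bleeding will carry much of the benefit-harm reading. If age predicts death, a test that ignores a balanced stratification factor is conservative and gives up some power.

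**Working it through.** **1. The plan's own figure.** The plan gives no size or power for secondary outcomes. Its only figure is 462 patients for the primary outcome (Protocol 7.1: 50% against 35%, 90% power, two-sided 0.05). Per arm, n = [1.960·√(2·0.425·0.575) + 1.282·√(0.50·0.50 + 0.35·0.65)]² / 0.15² ≈ 226.2, so 227 per arm and 454 in total. Hwang-Shih-DeCani spending with looks at 25% and 75% and an assumed gamma of −4 (the documents give none) inflates this by 1.017: 227 × 1.017 ≈ 231 per arm, or 462. Restoring age leaves this unchanged.

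**2. The texts side by side.**

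| Outcome type | Protocol 7.2 | SAP | Age in the SAP analysis? |
|---|---|---|---|
| Primary | Unadjusted chi-square | Unadjusted chi-squared, plus age-adjusted logistic (4.2) | Yes, as a complement |
| Binary secondary | Age-adjusted logistic | Chi-squared; odds ratio with no model named (4.3) | Not in the test; odds ratio not stated |
| Free-day outcomes | Age-adjusted linear | Ordinal logistic (4.3) | Not stated |
| D-dimer | Age-adjusted linear | Baseline-adjusted ANCOVA (4.3) | Not named |

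**3. Size of the unadjusted test for death.** Assumptions that are not in the documents: 60% of patients aged 65 or under, arms balanced within age strata, and the control death risks below. Let c be the stratum risk, w the stratum share and p = Σwc. The chi-squared test uses the variance V = p(1−p) per patient. Under stratified allocation the true null variance is W = Σw·c(1−c). The true two-sided size is 2Φ(−1.96·√(V/W)).

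| Control risk, ≤65 / >65 | p | V | W | V/W | Size |
|---|---|---|---|---|---|
| 6% / 15% | 0.096 | 0.0868 | 0.0848 | 1.023 | 4.7% |
| 4% / 20% | 0.104 | 0.0932 | 0.0870 | 1.071 | 4.3% |
| 3% / 25% | 0.118 | 0.1041 | 0.0925 | 1.126 | 3.8% |

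For example, at 4%/20%: p = 0.6·0.04 + 0.4·0.20 = 0.104; V = 0.104·0.896 = 0.0932; W = 0.6·0.04·0.96 + 0.4·0.20·0.80 = 0.0870; 1.96·√1.071 = 2.03; size 4.3%. Simulation agrees: across repeated runs the unadjusted size lay between 3.8% and 4.9%, against about 5% for the stratified test.

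**4. Power for death.** 462 patients, risk ratio 0.45 (assumed), 40,000 simulated trials per scenario, pooled two-proportion test against a Mantel-Haenszel test over the two age strata.

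| Control risk | Unadjusted | Stratified | Gain (points) |
|---|---|---|---|
| 6% / 15% | 61.5% | 62.2% | 0.7 |
| 4% / 20% | 65.3% | 67.1% | 1.8 |
| 3% / 25% | 72.4% | 74.9% | 2.5 |

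**5. Major bleeding.** With an assumed control risk of 2–5%, a conditional odds ratio of 2, age odds ratios of 1.5 to 6 and 40% of patients over 65, the unadjusted size is 5.0% to 4.6% and the power loss about 0.1 to 2 points.

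**6. What happens to the interval.** SAP 4.3 reports odds ratios. With age in the logistic model, the standard error of the log odds ratio goes up slightly: 0.386 to 0.394 at 4%/20%, and 0.364 to 0.379 at 3%/25%. The power gain arises because the conditional odds ratio lies further from 1. For instance, a conditional odds ratio of 0.50 corresponds to a marginal one of 0.50 to 0.54 for control death risks of 8–25% and age odds ratios of 1.5 to 6.

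**The case against.** The strongest reply is that little depends on this. The outcomes are exploratory under Protocol 7.2, and SAP 4.6 says the same of the secondary analyses. The error is conservative, so false positives are not inflated, and the loss is a few points of power at most. The SAP also says that it should be read together with the protocol, so its silence on covariates may be an omission rather than a decision. All of this stands as a limit on the importance of the point. It does not reconcile the documents for the binary outcomes, because a chi-squared test of independence cannot carry age however the two are read together.

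The documents do not support several stronger readings:

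- **That every secondary outcome is analysed unadjusted.** D-dimer is adjusted for its baseline value, and the covariates of the free-day models are unstated rather than excluded. The same holds for the model behind the binary odds ratios.
- **That the SAP leads with age adjustment for the primary outcome and abandons it for the rest.** The primary p-value, at the 0.048 level, also comes from an unadjusted test. The real difference is that the primary outcome receives an added age-adjusted model.
- **That ignoring age makes the reported intervals too wide.** On the log odds ratio scale the adjusted interval is the slightly wider one (step 6).
- **That age is certain to be available for every patient.** SAP 4.6 provides for imputing age if it is missing.

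One more objection is fair. For the free-day outcomes the protocol's continuous-outcome method is linear regression and the SAP's is ordinal, so adding age alone does not bring the two documents into line there.

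**Conclusion.** The point holds as a protocol-SAP discrepancy. Age adjustment, specified in Protocol 7.2, is named nowhere in SAP 4.3, and no reason is given. It is unambiguous for the binary outcomes, including death and major bleeding, and a matter of silence for the free-day models. For D-dimer, baseline is the only covariate named.

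The numerical consequence is small: for death, a true size of about 3.8–4.9% at a nominal 5%, and about 0.7–2.5 points of power. It is smaller still for rare outcomes at the same strength of age effect. These figures rest on the assumed age split, stratum risks and risk ratio. The discrepancy in the text rests on no assumption. No confirmatory conclusion and no sample size figure depends on it. It is worth correcting because the correction is nearly free, the protocol already specifies it, and two unreconciled analyses of mortality should not remain when results are reported.

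**What to change.** In SAP 4.3:

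- Make the age-adjusted logistic model of Protocol 7.2 the analysis of the binary secondary outcomes, with a Mantel-Haenszel estimate over the two age strata when events are sparse.
- Add age to the four ordinal logistic models and to the D-dimer ANCOVA.
- Keep crude proportions by arm as description.
- Label the adjusted odds ratios as age-conditional.
- State openly that ordinal regression replaces the protocol's linear regression for the free-day outcomes.

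If the sponsor prefers the unadjusted analyses, the minimum is to declare and justify the departure from Protocol 7.2 and to label the odds ratios as marginal.

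The cost is a few sentences and one covariate per model, with no new data collection and no change to the 462. Any missing age can follow the imputation provision in SAP 4.6, which would need extending because it now covers only the adjusted primary analysis. The small downside is a conditional odds ratio with a slightly wider log-scale interval; the gain is a test with close to its nominal size and a little more power.

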4.4 Subgroup Analysis

Subgroup analyses for the following characteristics at baseline will be conducted, accompanied by tests of treatment by subgroup interaction, using a logistic regression model.

The subgroups pre-specified in the protocol are as follows:

- Age (≤ 65 years versus > 65 years)
- Sex
- BMI ($\leq 30 \text{ kg/m}^2$ versus $> 30 \text{ kg/m}^2$)
- Time from COVID-19 symptom onset (≤ 7 days versus > 7 days since symptom onset)
- Diabetes mellitus
- Coronary artery disease
- Hypertension
- Race/ethnicity (Asian, Black or African American, Hispanic or Latino, White)

The following three pre-specified subgroups will also be analyzed (not pre-specified in the protocol):

- D-dimer levels at baseline ($< 2 \times$ upper limit of normal versus $\geq 2 \times$ upper limit of normal)
- Use of systemic corticosteroids at baseline
- Regions (North America, Brazil, Middle East, Ireland)

4.5 Sensitivity analysis

Sensitivity analyses will be performed (1) excluding those who did not have a follow-up until day 28, death, or other primary composite outcome component; (2) excluding those who did not satisfy all eligibility criteria; and (3) excluding both types of participants. Sensitivity analyses will be repeated in the PP subset, if different from the ITT population. If possible, the binomial model with identity link will be performed on the primary outcome as an additional sensitivity analysis.

To address changes in co-interventions over time due to emerging evidence from COVID-19 clinical trials, we will conduct a sensitivity analysis of the primary outcome using a logistic regression model with restricted cubic splines to model time by treatment interaction.

4.6 Missing data

The primary outcome will not have any missing data as per the definition of the ITT cohort above.

A multiple imputation approach may be applied to age as baseline characteristic for the adjusted analysis of the primary outcome in case of data missingness.

The secondary outcomes are also expected to be complete, or nearly complete since they are either components of the primary outcome or are measured in-hospital. Since secondary analyses are explorative, secondary outcomes will be analyzed as-is.

However, if a primary or secondary outcome is missing in more than 5% of randomized patients, a complete case analysis, an inverse probability weighted analysis and multiple imputation on outcome will also be conducted in addition to the primary strategies (see Sections 4.2 and 4.3).
